3.2.10.2 Exposure-response Analysis of Efficacy (ORR) and Safety (ILD)

There was a dose and E-R relationship observed for ORR in Study 101 over the dose range 0.68 to 1.2 mg/kg Q3W in participants with PROC, which was the tumor type with the largest number of patients enrolled (n = 58). There was also a dose and E-R relationship observed for ILD when data were combined across tumor types from Studies 101 and 201 (N = 96 total; n = 81, Study 101 and (including both escalation and expansion) had the highest ORR of 54.2% (13/24) in PROC and highest ILD rate of 58.3% (14/24) across tumor types. The next lower dose level, 0.9 mg/kg Q3W, led to a lower ORR of 32.1% (9/28) and ILD rate of 37.0% (17/46) in Study 101.

An E-R efficacy (ORR) analysis was conducted with participants with PROC from Study 101 (n = 58). Across the dose range of 0.3 to 1.2 mg/kg Q3W, 21 participants had a PR, and 2 participants had a CR with an ORR of 39.7% (23/58). Exposure (area under the concentration-time curve [AUC]) was the only significant predictor of the probability of an objective response (OR) in a multivariate logistic regression analysis. Age, weight, non-HGS (vs HGS OC), and Eastern Cooperative Oncology Group performance status (ECOG PS; 1 vs 0) were not significant predictors of an OR. Higher doses above 1.2 mg/kg Q3W would be expected to result in a higher probability of an OR, given linear PK and lack of saturation of OR across the current dose range. Based on the results of the E-R analysis, clinically meaningful efficacy is expected across the dose range of 0.68 to 1.2 mg/kg.

range of 0.68 to 1.2 mg/kg.

An E-R analysis of all grade ILD by expert review was conducted including participants from Study 101 across the dose range of 0.3 to 1.2 mg/kg Q3W and from Study 201 across the dose range of 0.9 to 1.2 mg/kg Q3W (N = 96 participants in total). Forty-eight participants had ILD identified by expert review for an ILD rate of 50% (48/96) across the studies and dose range. In a multivariate analysis, AUC and age were significant predictors of ILD, with both higher AUC and

Protocol Amendment No.: 03 Date: 07-Apr-2023

higher age predicting a higher probability of ILD. ⁵⁰	

[figure not shown]
3.2.10.4 Corrected QT Interval Assessment

msec. While single-agent eribulin mesylate at the prescribed dose of 1.4 mg/m² prolonged QTc, with a maximum mean QTcF change from baseline (95% upper confidence interval) of 11.4 msec (19.5) in 26 patients with solid tumors, there was no concentration effect identified. The total dose of eribulin (unconjugated) at the highest MORAb-202 dose evaluated (1.2 mg/kg Q3W) is 0.85 mg/m², which is 1.6-fold lower than the approved eribulin single-agent dose of 1.4 mg/m². These data combined with plasma levels of released eribulin from MORAb-202 that are approximately 300-fold lower than with single-agent eribulin, indicate a low risk of QTc prolongation for MORAb-202. Therefore, for all treated participants, electrocardiograms (ECGs) will only be required at baseline and at end of treatment (EOT). During study treatment and safety follow-up, ECGs should be performed as clinically indicated.

3.3 Benefit/Risk Assessment

Overall, the observed safety profile of MORAb-202 has been manageable and generally consistent across clinical trials, with no MTD reached at dose levels up to 1.2 mg/kg.

(see Section 3.2.6). As described in Section 3.2.6, clinical activity with MORAb-202 treatment was observed across multiple FR\alpha-expressing tumor types. Across Studies 101 and 201, 107 participants were exposed to MORAb-202 as of the cutoff date of 31-Aug-2021, including 20 participants with participants have received MORAb-202 in Study 201 in the dose confirmation part, after the data cutoff date of 31-Aug-2021. Clinical responses were observed in participants with tumors across FR\alpha-expression levels at different MORAb-202 dose range levels; however, lower rates of all grade ILD have been observed with lower doses while a trend was observed for higher grade ILD in participants with higher BW. In order to reduce the overall rate of ILD and high-grade ILD,

Based on clinical study experience to date, ILD/pneumonitis associated with MORAb-202 appears to be responsive to treatment with corticosteroids. ⁵² For some participants who experienced

. AEs due to steroid use in Study 101 were generally not reported, which is in line with current clinical experience with steroid use as a treatment for AEs in cancer patients. 53,54

Lastly, the recommendations for monitoring and management of ILD/pneumonitis included in this study have been revised since the initial recommendations implemented in Studies 101 and 201, based upon thorough analyses of clinical data from participants who experienced events of MORAb-202-related ILD/pneumonitis (refer to Section 7.4.1 for ILD/pneumonitis management recommendations).

See Section 3.2.8 for further details on overall safety profile observed in MORAb-202 clinical trials.

More detailed information about the known and expected benefits and risks and reasonably anticipated AEs of MORAb-202 may be found in the current MORAb-202 Global IB. 15

The global coronavirus disease 2019 (COVID-19) pandemic has been identified as a potential risk to clinical study participants in general and may particularly affect individuals with underlying chronic diseases on immunomodulatory therapies. In general, participants with lung cancer are at an increased risk for respiratory compromise. As described in the Global IB and informed consent form (ICF), MORAb-202 is an immunomodulatory Investigational Medicinal Product (IMP) with the potential for immunosuppressive effects. Based on the mechanism of action, infections are a potential risk. It is not known whether taking MORAb-202 increases the risk of severe acute respiratory syndrome coronavirus 2 (SARS-CoV-2) infection, or the duration or severity of COVID-19 disease. The inclusion criteria (Section 6.1) have been designed to exclude people with current and recent infections. Testing to exclude asymptomatic SARS-CoV-2 prior to enrollment should follow local standard practice. The study has been designed with study visits that allow for close monitoring of participants' safety throughout the clinical study (Section 2), and participants are encouraged to contact the investigator if an intercurrent illness develops between study visits. Testing for COVID-19 to inform decisions about clinical care during the study should follow local standard practice. In addition, the Sponsor has also developed guidance for investigators on how to manage a participant with a clinical suspicion of, or a diagnosis of, COVID-19. This includes criteria for temporarily interrupting or permanently discontinuing IMP (Section 8.1), and criteria for reinitiating IMP on resolution of a COVID-19 infection (Section 8.1). In order to facilitate enhanced reporting of COVID-19 events that occur during the study, all AEs and SAEs reported after the time of consent that are related to SARS-CoV-2 or COVID-19 infection must be reported (Section 9.2). Individual benefit-risk considerations remain the responsibility of the investigator. Investigators should apply clinical judgment and these risks should be considered when enrolling a participant. With respect to the benefit/risk of receiving COVID-19 vaccinations during treatment with MORAb-202, non-live COVID-19 vaccination is considered a concomitant medication within the study. However, the efficacy and safety of non-live vaccines (including non-live COVID-19 vaccines) in participants receiving MORAb-202 is unknown.

Refer to the risk assessment Section 3.3.1 for identified risks and mitigation strategy.

3.3.1 Risk Assessment

Table 3.3.1-1: Risk Assessment

Potential Risk of Clinical Significance	Summary of Data/ Rationale for Risk	Mitigation Strategy
Study Intervention(s)		
Interstitial Lung Disease (ILD)/pneumonitis.	MORAb-202 Global Investigator's Brochure (IB)	Eligibility criteria, consistent monitoring (eg, pulse oximetry, signs/symptoms), dosing of MORAb-202 to limit exposure variance in participants with higher body weight, investigator/site training on ILD/pneumonitis detection and management, participant alert card, Safety Committee continuous safety monitoring, ILD Expert Review Committee. These mitigation measures, together with the use of is expected to improve toxicity profile of MORAb-202 and its benefit/risk ratio.
Infusion-related reactions	MORAb-202 Global IB	Premedications for first MORAb-202 infusion, eligibility criteria; close monitoring for hypersensitivity/allergic reactions during MORAb-202 infusions, secondary prophylaxis. Guidelines for management and dose modification are included in Section 7.4.
Aspartate aminotransferase (AST) / alanine aminotransferase (ALT) elevations	MORAb-202 Global IB	Eligibility criteria, monitoring with predose evaluation of liver enzymes at each cycle. Guidelines for management and dose modification are included in Section 7.4.
Nausea	MORAb-202 Global IB	Monitoring at each cycle. Guidelines for dose modification are included in Section 7.4. Management per institutional protocol/investigator discretion.
Ругехіа	MORAb-202 Global IB	Monitoring at each cycle. Guidelines for dose modification and recommended management algorithm is included in Section 7.4. Management or as per institutional protocol/investigator discretion.
Potential reproductive toxicity	MORAb-202 Global IB	Eligibility criteria, pregnancy testing, contraception per Sections 6.1 and 9.2.5, and Appendix 4.

Protocol Amendment No.: 03

Date: 07-Apr-2023

Approved v4.0 930184408 4.0

Table 3.3.1-1: Risk Assessment

Potential Risk of Clinical Significance	Summary of Data/ Rationale for Risk	Mitigation Strategy	
Study Procedures			
Blood draws/use of intravenous catheter for laboratory assessments (eg, pain, bruising, bleeding, infection, fainting)		Per institutional protocol/investigator discretion.	
CT scan/ magnetic resonance imaging (MRI) radiation exposure		Per institutional protocol/investigator discretion.	
Allergy to contrast agent for CT scan/MRI (eg, allergic reaction, anaphylaxis)	Contrast United States Prescribing Information and Summary of Product Characteristics	Prophylaxis and/or treatment per institutional protocol/investigator discretion.	
Other (if applicable)			
Severe acute respiratory syndrome coronavirus 2 (SARS-CoV-2) infection	Policy and guidance for the conduct of BMS-sponsored clinical research in light of SARS-CoV-2	See exclusion criteria (Section 6.2), rescreening criteria (Section 6.4.1) and dose modifications (Section 7.4.1) sections for SARS-CoV-2 Safety Surveillance Plan.	
Dosing delay due to SARS-CoV-2 lockdowns	BMS SARS-CoV-2 Clinical Research Project Management Office	Specific measures have been considered to ensure the study can continue should the hospital be subject to increased demands/restrictions due to the pandemic (travel restrictions, remote access / monitoring, preventative measures, etc).	

Protocol Amendment No.: 03

3.3.2 Benefit Assessment

There is currently an unmet medical need for safe and effective therapy for patients with advanced NSCLC who have progressed on currently approved therapies. Existing data suggest promising clinical activity with MORAb-202 in participants with FR α -expressing advanced cancers. Safety and efficacy are primary endpoints of this study. Safety will be monitored on an ongoing basis by the clinical study team, the pharmacovigilance team and various oversight committees.

MORAb-202 may address this high unmet need for patients with NSCLC AC, given its unique, tumor-specific mechanism (ie, FR α -directed ADC), the high prevalence of FR α overexpression in lung cancer, and the preclinical and clinical activity seen to date (see Section 5.4.1). See Section 5.4.2 for further details on clinical efficacy in MORAb-202 studies.

The additional medical surveillance provided by a clinical trial translates into close monitoring of the participants for toxicities and promotes prompt identification and adequate treatment of AEs.

3.3.3 Overall Benefit/Risk Conclusion

Considering the measures taken to minimize risk to participants in this study, the potential risks identified in association with MORAb-202 ILD/pneumonitis are justified by the anticipated benefits that may be afforded to participants with previously treated, metastatic NSCLC AC.

The Sponsor will evaluate the benefit/risk profile of the study intervention on an ongoing basis. This evaluation will be based on all available data, with particular attention to: (i) AEs including ILD/pneumonitis or other safety trends in this or any other clinical study of MORAb-202 where character, severity, and/or frequency suggest that participants would be exposed to an unreasonable and significant risk of illness or injury; (ii) new nonclinical data suggesting unreasonable and significant risk of illness or injury.

If such evaluation suggests that the benefit/risk profile of the study intervention has become unfavorable to participants, the Sponsor will pause enrollment and/or treatment until further evaluation of data and communicate with the appropriate Health Authority(ies) on potential actions. Such actions may include (but are not limited to) study continuation, substantial amendment, or termination of the study.

In conclusion, the overall benefit/risk of MORAb-202 in participants with previously treated, metastatic NSCLC AC is assessed to be acceptable and is described further in the following sections.

Protocol Amendment No.: 03

930184408 4.0

Approved v 4.0

4 OBJECTIVES AND ENDPOINTS

Table 4-1: Objectives, Endpoints and Estimands

Objectives	Endpoints	
Primary	Primary	
To assess safety and tolerability of MORAb-202 in participants with previously treated, metastatic non-small cell lung cancer (NSCLC) adenocarcinoma (AC)	Incidence of treatment-related adverse events (TRAEs) leading to study treatment discontinuation	

Main Estimand for the Primary Objective^a

- Treatment: MORAb-202, 25 mg/m²
- Population: Participants with previously treated, metastatic NSCLC AC
- Variable: Occurrence of TRAEs leading to study treatment discontinuation
- Intercurrent events: Early discontinuation of study treatment due to reasons other than TRAE leading to treatment discontinuation
 - Strategy to handle intercurrent events: While on treatment (early discontinuation of treatment due to reasons other than TRAEs would not be counted towards population-level summary)
- Population-level summary: Adverse event (AE) incidence rate;
- To assess tumor response of MORAb-202 in participants with previously treated, metastatic NSCLC AC
- Objective response rate (ORR) by Response Evaluation Criteria in Solid Tumors (RECIST) 1.1 per investigator assessment

Main Estimand for the Primary Objective^a

- Treatment: MORAb-202, 25 mg/m²
- Population: Participants with previously treated, metastatic NSCLC AC with evaluable baseline tumor assessment
- Variable: Best overall response (BOR), defined as the best response, as determined by investigator, recorded between the date of first dose and the date of first objectively documented progression per RECIST 1.1
- Intercurrent events: Early discontinuation of study treatment
 - Strategy to handle intercurrent events: Treatment policy (all post-baseline tumor assessment regardless of on-treatment status will contribute to BOR determination)
- Intercurrent events: Initiation of subsequent anticancer therapy (excluding allowed palliative radiotherapy/surgery to non-target/non-thoracic sites)
 - Strategy to handle intercurrent events: Treatment policy (all post-baseline tumor assessment regardless of initiation of subsequent anticancer therapy will contribute to BOR determination)

Protocol Amendment No.: 03

Table 4-1: Objectives, Endpoints and Estimands

	Objectives	Endpoints	

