Doses of MORAb-202 may be reduced, interrupted, delayed, or discontinued depending on how well the participant tolerates the treatment, as specified in the protocol.

Safety follow-up visits will be conducted 30 days after the last study drug administration. All ongoing treatment-related serious AEs and ILD events will be followed until resolution or stabilization. Survival follow-up visits will occur every 3 months (± 14 days) from safety follow-up, for up to 2 years, or until death, loss to follow-up, withdrawal of consent, or conclusion of the study, whichever occurs first. All participants discontinuing treatment for reasons other than disease progression will be followed for continued tumor assessments until investigator-assessed disease progression per Response Evaluation Criteria in Solid Tumors 1.1, death, or withdrawal of consent for tumor assessment, whichever occurs first.

End of study is defined as all treated participants who complete their last visit or scheduled procedure. Study completion is defined as the final date on which data for the endpoint of overall

Protocol Amendment No.: 03

survival were or are expected to be collected if this is not the same. A participant is considered to have completed the study if he/she has completed all survival follow-up visits.

Study Intervention:

Name					
Intervention Name/ Unit Dose Strength(s)	MORAb-202 (BMS-986445)/ [mg/ml]				
Туре	Drug				
Dose Formulation	Lyophilized powder in a single use vial				
Dosage Level(s)	$25 \text{ mg/m}^2 \text{ Q3W}$				
Route of Administration	IV infusion				
Use	Experimental				
IMP and NIMP/AxMP	IMP				
Sourcing	Provided centrally by the Sponsor				

Abbreviations: AxMP, auxiliary medicinal product; IMP, investigational medicinal product; IV, intravenous; NIMP, non-investigational medicinal product; Q3W, every 3 weeks.

Statistical Methods:

The primary endpoints are being assessed based on a targeted

The primary analysis will be performed when all participants in each arm have been followed up for a minimum of 6 months or discontinued earlier from treatment.

Data Monitoring Committee: No

A Data Monitoring Committee will not be used in the study.

Other Committee: Yes

A SC, and SSC will be used in this study.

Brief Summary:

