relevant data (safety, efficacy, PK, and pharmacodynamics) will inform the Sponsor's decision on subsequent clinical development, including enrollment of additional participants into an expansion cohort to assess the relationship with FR α expression through a protocol amendment or continuing development in a separate study (see Section 10.1).

The primary analysis will be performed when all participants have been followed up for a minimum of 6 months or discontinued earlier from treatment. One dose level of MORAb-202 will be selected at the primary analysis to continue further evaluation. The dose selection will be based on the totality of efficacy and safety data and as described in Section 10.1. Safety follow-up visits will be conducted 30 days after the last study drug administration. All ongoing treatment-related SAEs and ILD/pneumonitis events will be followed until resolution or stabilization. All participants discontinuing treatment for reasons other than disease progression will be followed for continued tumor imaging assessments until investigator-assessed disease progression per RECIST 1.1, death, or withdrawal of consent for tumor assessment, whichever occurs first. All participants will be followed for survival every 3 months until the last participant has completed 2 years of survival follow-up.

The study design schematic is presented in Figure 5.1-1.

Figure 5.1-1: Study Design Schema

Physical examinations, vital sign measurements, and clinical laboratory evaluations will be performed at selected times throughout the treatment period. Participants will be closely monitored for AEs throughout the study. Blood samples will be collected for PK analysis. See Section 2 for more detail.

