5.4.1 Rationale for Choice of Endpoints

ORR is an accepted Phase 2 endpoint in NSCLC studies that allows data to be assessed earlier and in a smaller study population compared with survival-based endpoints. ORR allows the effect to be attributed to a single regimen, removed from subsequent therapies.⁵⁷ Furthermore, clinical data for MORAb-202 has shown significant cytotoxicity and tumor reduction. The mechanism of action of the drug indicates direct activity on the tumor, hence ORR is an appropriate measure of activity in this dose-finding study. In this study, ORR will be assessed by the investigator using RECIST 1.1 to avoid delays in implementation of subsequent intervention in this advanced cancer

setting. The tumor response will be further described by the durability of responses. Safety and tolerability are a co-primary endpoint to allow selection of the dose with the optimal benefit/risk profile.

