7.7 Concomitant Therapy

7.7.1 Palliative Local Therapy

Palliative local therapy, including palliative radiation therapy and palliative surgical resection, to symptomatic non-target lung lesions (ie, causing hemoptysis or obstruction), bone lesions, skin lesions, or CNS lesions is permitted prior to discontinuation of study treatment for participants who do not have evidence of overall clinical or radiographic progression, per RECIST 1.1. Any palliative radiation therapy where the radiation field involves the lung (ie, chest wall, thoracic spine, mediastinum, esophagus, lung, etc), should first be discussed with and approved by the Medical Monitor/designee.

Participants requiring palliative local therapy should be evaluated for objective evidence of disease progression prior to the initiation of such therapy. If progression, per RECIST 1.1 by investigator assessment, is identified on any tumor assessments prior to the initiation of palliative local therapy, then participants must discontinue study drug treatment.

The potential for overlapping toxicities with radiotherapy and MORAb-202 currently is not known. As concurrent radiotherapy and MORAb-202 have not been evaluated, in cases where palliative radiotherapy is required for a tumor lesion, then it is recommended that MORAb-202 dosing is held prior to initiation of radiation therapy. Participants should be closely monitored for any potential toxicity during and after receiving radiotherapy, and AEs should resolve to $Grade \leq 1$ prior to resuming study drug.

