10.3.2 Efficacy Analyses

Endpoint	Statistical Analysis Methods	
Primary Analyse	es	
ORR by Response Evaluation Criteria in Solid Tumors (RECIST) 1.1 per investigator assessment	Objective Response Rate (ORR) is defined as the number of participants who achieve a best overall response (BOR) of confirmed complete response (CR) or confirmed partial response (PR), based on investigator assessments (using RECIST 1.1), divided by the number of all response-evaluable participants. BOR is defined as the best response, as determined by the investigator, recorded between the date of first dose and the date of first objectively documented progression per RECIST 1.1. For participants without documented progression or subsequent therapy, all available response designations will contribute to the BOR determination. The number and percentage of participants in each category of BOR per investigator (complete response [CR], partial response [PR], stable disease [SD], progressive disease [PD], or unable to determine [UTD]) will be presented. Estimates of response rate, along with its exact two-sided 95% confidence interval (CI) by Clopper and Pearson ⁷⁰ will be presented.	
Secondary/ Analyses		
PFS by RECIST 1.1 per investigator assessment	PFS is defined as the time between the date of first dose and the first date of documented progression, per investigator assessments (using RECIST 1.1), or death due to any cause, whichever occurs first. Participants who did not progress or die will be censored on the date of their last evaluable tumor assessment. Participants who did not have any on study tumor assessments and did not die will be censored on their date of first dose. The PFS function will be estimated using the KM product limit method and will be displayed graphically. A two-sided 95% CI for median PFS will be computed via the log-log transformation method. PFS rates at fixed time points (eg, 3, 6 months, depending on the minimum follow-up) will be presented along with their associated 95% CIs. These estimates will be derived from the Kaplan Meier estimate and corresponding CIs will be derived based on Greenwood's ⁷¹ formula for variance derivation and the log-log transformation applied on the survivor function ⁷² .	

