2.3 Response Assessment

2.3.1 Evaluation of Best Overall Response

The best overall response is the best response recorded from the start of the study treatment until disease progression or the last response recorded, taking into account any requirement for confirmation and censoring rules regarding subsequent therapy. The patient's best overall response assignment will depend on the findings of both target and non-target disease and will also take into consideration the appearance of new lesions. Furthermore, depending on the nature of the study and the protocol requirements, it may also require confirmatory measurement.

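### For participants who switch before progression, Table 4-1 counts a response on the next anticancer therapy as a MORAb-202 response, against Section 5.4.1's stated reason for using ORR

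*Combined protocol and SAP*

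**What the plan says.** - **Table 4-1, ORR row.** BOR runs from first dose to first documented progression. Starting another anticancer therapy is an intercurrent event handled by treatment policy: "all post-baseline tumor assessment regardless of initiation of subsequent anticancer therapy will contribute to BOR determination". The DCR row uses the same strategy. Some local treatment does not count as this event: "excluding allowed palliative radiotherapy/surgery to non-target/non-thoracic sites".
- **Section 5.4.1.** The reason given for the endpoint is: "ORR allows the effect to be attributed to a single regimen, removed from subsequent therapies".
- **Section 10.3.2.** BOR is first defined over the same window as in Table 4-1. The text then adds: "For participants without documented progression or subsequent therapy, all available response designations will contribute to the BOR determination".
- **Appendix 6, Section 2.3.1.** BOR is assigned "taking into account any requirement for confirmation and censoring rules regarding subsequent therapy".
- **Imaging after study drug stops.** The Protocol Summary states: "All participants discontinuing treatment for reasons other than disease progression will be followed for continued tumor assessments until investigator-assessed disease progression". Section 5.1 gives the end points for this imaging: "until investigator-assessed disease progression per RECIST 1.1, death, or withdrawal of consent for tumor assessment, whichever occurs first".
- **Section 7.7.1.** Palliative local treatment of "symptomatic non-target lung lesions (ie, causing hemoptysis or obstruction), bone lesions, skin lesions, or CNS lesions is permitted prior to discontinuation of study treatment", provided that there is no overall progression.
- **Table 4-1, footnote a.** Sensitivity estimators and supplemental estimands are left to the SAP. The main estimand is not.

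**The concern.** ORR is one of two primary endpoints, and the current text describes one dose and no control arm, so nothing offsets a response produced by another drug. The protocol chose ORR to isolate one regimen, yet its main estimand does not isolate it for participants who switch before progression. They are a foreseeable group. Treatment-related discontinuation is the other primary endpoint, and Section 8.1 lists several reasons for stopping other than progression. Their scans will exist, because starting new therapy does not end imaging.

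A programmer deriving BOR for such a participant would find a clear instruction in Table 4-1, a sentence in Section 10.3.2 that appears to set the participant apart, and a pointer in Appendix 6 to rules that are not there.

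**Working it through.** There is no stated figure to reproduce. The sample size and the targets in Section 10.1 are not visible.

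**1. One participant under each passage.** Suppose SD at Week 6, study drug stopped for toxicity, another therapy started without progression, and PR at Weeks 18 and 24.

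| Source | Result for this participant |
|---|---|
| Table 4-1 | Responder: all scans up to progression count |
| Section 10.3.2, general definition | Responder: same window, no cut at new therapy |
| Section 10.3.2, next sentence | Does not cover the participant, who has had subsequent therapy; no other rule follows |
| Appendix 6, 2.3.1 | Depends on censoring rules not defined in the visible text |
| Section 5.4.1, rationale | The response should not be attributed to MORAb-202 |

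**2. Direction.** A cut-off at new therapy removes scans from the end of the window. Removing them cannot create a confirmed response or disease control, and cannot undo one already established. The present rule therefore gives an ORR and DCR equal to or higher than the cut-off would. Only participants who switch before progression without a confirmed response (ORR), or without qualifying disease control (DCR), can differ.

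**3. Illustrative size for ORR.** Rise = share switching before progression without a confirmed response × response rate on the next therapy. The share is assumed. The rate is the 6.8% to 14% quoted for docetaxel in Section 3.2.1.

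| Assumed share | × 0.068 | × 0.14 |
|---|---|---|
| 5% | 0.34 points | 0.70 points |
| 10% | 0.68 points | 1.40 points |
| 20% | 1.36 points | 2.80 points |

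**4. In whole participants.** At an assumed n = 40 with 8 such switchers, the chance of at least one credited response is 1 − 0.932^8 = 43% at the lower rate and 1 − 0.86^8 = 70% at the higher. One extra responder would move 8/40 = 20.0% (exact 95% CI 9.1 to 35.6) to 9/40 = 22.5% (10.8 to 38.5). At an assumed n of 30 or 60, one participant is worth 1/30 = 3.3 or 1/60 = 1.7 points.

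**5. A separate case: PR first seen on MORAb-202 but confirmed only after a switch.** Body imaging is every 6 weeks to Week 36, then every 12 weeks, and Appendix 6, 2.3.4 allows one intervening time point. On scheduled scans the confirming scan comes:
- 6 or 12 weeks later if the response is first seen by Week 24;
- 6 or 18 weeks later if first seen at Week 30;
- 12 or 24 weeks later if first seen from Week 36.

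The ±7-day window and unscheduled scans can shift these gaps. A switch can fall inside them, so a cut-off would drop some responses that began on MORAb-202. Their number cannot be derived.

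**The case against.** The best defence is that treatment policy is legitimate and looks deliberate. It is applied throughout to ORR, PFS, DCR and DoR, and the change history records that Amendment 02 revised the estimands to clarify intercurrent events. On this view Section 5.4.1 is a general rationale, given beside a contrast with survival-based endpoints, and does not define the estimand. With the window closed at progression, ORR is still largely separate from later therapy. Appendix 6 reads as template text, so its reference to censoring rules may be only an unfilled placeholder. The SAP that Sections 10.1 and 10.3.1 refer to is not in the supplied text and might define such rules.

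Much of this stands, and it rules out several stronger readings:

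- A reader might infer that any response to a later drug is credited. It is not, because BOR ends at first documented progression.
- A reader might infer that Section 10.3.2 or Appendix 6 sets a competing cut-off. Neither does, and the general definition in Section 10.3.2 matches Table 4-1.
- A reader might infer that the difference between Table 4-1 and Section 7.7.1 on palliative treatment biases ORR now. It does not: under treatment policy all scans count either way. It matters only once a cut-off is adopted.

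The defence does not remove the mismatch for participants who switch before progression. The single-regimen reason is the protocol's own, and the main estimand departs from it for this group. Footnote a does not leave the main estimand to the SAP.

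**Conclusion.** The point holds for participants who start another therapy before progression. The main ORR and DCR estimands credit MORAb-202 with response or disease control first recorded on that therapy, contrary to the stated purpose of ORR. Sections 10.3.2 and Appendix 6 need aligning whichever rule is kept.

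The direction is certain relative to a cut-off; the size is not. The 0.3–2.8 points of ORR rest on an assumed 5–20% of participants switching without a confirmed response, and on docetaxel rates not established for people who switch before progression and are measured against their pre-MORAb-202 baseline. The range is an illustration, not a bound, and the DCR effect is not sized. A reader might infer a materially inflated ORR; the documents do not support that, and the effect is probably small. It should still be settled before database lock, because Section 5.1 has efficacy inform further development.

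**What to change.** Put one BOR rule in Table 4-1 (ORR and DCR rows), Section 10.3.2 and Appendix 6, 2.3.1: *BOR is the best response from first dose to the earlier of first documented progression or the start of subsequent anticancer therapy; a participant with no confirmed response in that window is a non-responder for ORR.* In addition:

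- For BOR only, let permitted palliative local therapy leave the window open only where it does not involve a target lesion. Exempting everything that Section 7.7.1 allows could let local treatment of a target lesion count as a drug response. Reconcile the site wording of Table 4-1 with Section 7.7.1 without changing what Section 7.7.1 permits.
- Report two supplementary analyses: the present treatment-policy version, and one that also counts responses first seen on MORAb-202 but confirmed after a switch.
- Use the same responder set for DoR, and state how DoR handles later therapy.
- Keep treatment policy for early discontinuation of study drug.
- Confirm that the CRF records the start date of subsequent therapy. Table 2-3 collects the therapy and the response to it, but does not name the date.

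The cost is wording in three places and the SAP, two extra tables, and possibly one date field. ORR may be slightly lower, and responses begun on MORAb-202 but confirmed only after a switch would appear only in the supplementary analyses.

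If the sponsor keeps treatment policy as the main estimand, it should state this in Section 10.3.2 and Appendix 6, revise Section 5.4.1, and add the cut-off version as a supplementary analysis. That restores consistency but gives up the single-regimen question.
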